There is a high variation in individual phenotype makes BMI a poor predictor of adiposity-level and risk, especially among women and some ethnic groups (14). Meta-analysis of studies in non-pregnant populations shows that using obese BMI criteria only identifies 50% of adults with excess adiposity, as BMI cannot distinguish between fat mass and lean mass, whereas measures of body fat distribution can distinguish individuals' mortality and cardiometabolic risk (15, 16).

Failure to predict pregnancy risk results in harm for mother and child and increases healthcare costs. Furthermore, inaccurate risk communication can increase anxiety and distress, as well as waste care. There is an urgent need to identify measures of adiposity-related risk with greater sensitivity and specificity than BMI to inform targeted high-risk care to improve health of women and offspring and reduce waste of NHS resources.

This prospective cohort study will measure alternative (to BMI) indicators of obesity/adiposity in pregnant women to explore the ability of these markers to predict adverse pregnancy outcomes. A range of alternative adiposity measures exist, which can be assessed using a number of different anthropometric measures (for example, waist circumference, neck circumference) or ultrasound/MRI scans (for example to identify abdominal subcutaneous and visceral fat volumes). Some of these measures (e.g. MRI scans) are costly and impractical for implementation into routine pregnancy care. This study will focus on the measurement of indicators of obesity that it would be feasible to implement in routine NHS maternity care.

This study is one part of a larger body of work that seeks to address the question of if there are more cost-effective adiposity measures than BMI to allocate high-risk care in pregnancy.

7. Research question, aim and objectives

Are there alternative adiposity measures to BMI which better predict adverse pregnancy outcomes?

Aim

To evaluate the prognostic performance of single adiposity measures or a multivariable model to estimate risk of adverse pregnancy outcomes.

Objectives

1. To identify the prognostic value of single adiposity measures for predicting adverse maternal, fetal and neonatal outcomes (for each outcome of interest separately, and as a composite outcome)
2. To develop a prognostic model to investigate the effect of including multiple adiposity, socio-demographic and clinical predictors on the accuracy of predicting outcomes

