3. To test the predictive performance of the prognostic measures/models using calibration, discrimination and internal validation techniques.

8. Plan of investigation

a. Design

Prospective cohort study. Pregnant women will be recruited at 11⁺² to 14⁺¹ weeks' gestation (dating scan). Baseline adiposity measures and other potential predictor variables of interest for a multi-variable model (including clinical and socio-demographic data) will be collected from women at this time or from hospital records. Data on outcome of pregnancy will be collected from hospital records after delivery.

b. Population

Pregnant women attending the Royal Victoria Infirmary (RVI), Newcastle upon Tyne NHS Trust (NUTH) for a 1st trimester scan (conducted at 11⁺² to 14⁺¹ weeks' gestation; hereafter referred to as the "12-week scan").

c. Inclusion and exclusion criteria

Inclusion criteria

- Singleton pregnancy (women who consent to participate but who are subsequently found to have a multiple pregnancy will be excluded)
- ≥ 18 years of age

- Approximately 12 weeks' gestation (11⁺² to 14⁺¹ weeks)
- Planned delivery at NUTH

Exclusion criteria

- Unable/unwilling to give informed consent to participate
- Women with a miscarriage prior to the 12-week scan, or threatened miscarriage identified on the patient's records as a visit to the Early Pregnancy Assessment Clinic (EPAC) or A&E relating to their pregnancy with an adverse outcome, will be excluded.
- Women having twins (or higher order pregnancy) - we will not know whether women have a multiple pregnancy until their 12 week scan appointment (after consent). Any women identified as having a multiple pregnancy at the 12-week scan will be excluded. They will still receive the thank you gift of pregnancy photographs.

d. Recruitment procedure

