The table provided in Appendix 2 indicates which additional predictor variables are available from routine records and which will be collected by questionnaire during the 12-week scan appointment. A member of the research team will be available to answer any queries that the participants have related to the completion of the questionnaire.

Outcomes

Adverse outcomes of interest are:

- Gestational diabetes; defined as fasting plasma glucose level of ≥ 5.6 mmol/litre or 2 hour plasma glucose level of ≥ 7.8 mmol/litre

- Gestational hypertension; defined as blood pressure $\geq 140/90$ mmHg on two occasions at least 4 hours apart after 20 weeks' gestation
- Preeclampsia; defined as a new onset of hypertension (>140 mmHg systolic or >90 mmHg diastolic) after 20 weeks of pregnancy with a new onset of proteinuria or/and maternal organ dysfunction or/and uteroplacental dysfunction. Early onset defined as onset of PE before 34 weeks gestation.
- Metabolic syndrome: diagnosed using 3 of the following measures: overweight/obese BMI or high waist circumference, elevated triglycerides, high blood pressure that's consistently 140/90mmHg or higher, insulin resistance.
- Pre-term birth; defined as birth before 37 weeks gestation
- Late-term birth; defined as pregnancy that extends over 41 weeks gestation
- Induction of labour; defined as non-surgical treatment to induce the labour.
- Caesarean section; defined as surgical delivery of baby (emergency or elective)
- Instrumental delivery; defined as an assisted birth when forceps or a ventouse suction cup is applied
- Retained placenta: as reported in medical records.
- Haemorrhage: 3rd stage of labour and immediate postpartum period, measured in ml blood loss; as reported in medical records.
- Maternal infection: as reported in medical records.
- Fetal growth: measured at 2nd and 3rd trimester scans, including:
 - o 2nd trimester scan: Fetal head circumference; Fetal abdominal circumference; Fetal Femur Length; Estimated fetal weight Hadlock; as reported in medical records.
 - o 3rd trimester scan: abdominal circumference; Femur Length; Estimated fetal weight Hadlock; Umbilical artery PI; End Diastolic flow; Amniotic Fluid Index; as reported in medical records.
- Large for gestational age; defined as birth weight above the 90th centile for gestational age and sex on INTERGROWTH chart.
- Small for gestational age; defined as birth weight below the 10th centile for gestational age and sex on INTERGROWTH chart.

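### Maternal infection has no time window and no recorded date, so infections from before the 12-week measurement are not excluded from an outcome that the measurement is meant to predict

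*Protocol*

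**What the plan says.** The aim is prognostic. Objective 1 in Section 7 reads "To identify the prognostic value of single adiposity measures for predicting adverse maternal, fetal and neonatal outcomes", separately for each outcome and as a composite.

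Section 8a places the predictors at the 12-week scan (11+2 to 14+1 weeks): "Baseline adiposity measures and other potential predictor variables of interest for a multi-variable model (including clinical and socio-demographic data) will be collected" at that time or from hospital records. On outcomes it says "Data on outcome of pregnancy will be collected from hospital records after delivery".

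In the outcome list of Section 8f the whole definition is "Maternal infection: as reported in medical records". Other maternal outcomes in the same list carry a time limit:

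- gestational hypertension: "on two occasions at least 4 hours apart after 20 weeks' gestation"
- pre-eclampsia: new hypertension "after 20 weeks of pregnancy with a new onset of proteinuria" or other specified dysfunction
- haemorrhage: "Haemorrhage: 3rd stage of labour and immediate postpartum period, measured in ml blood loss"

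Appendix 2 collects gestation at diagnosis for gestational diabetes and gestation at onset for pregnancy-induced hypertension and pre-eclampsia. Maternal infection is a single item from electronic records, with no date or gestation. The exclusion criteria in Section 8c do not mention infection.

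**The concern.** A prognostic outcome has to arise after the point of prediction. Most outcomes in Section 8f do so by nature, because they concern delivery, birthweight or the newborn. Maternal infection does not: it can occur, be treated and be recorded at any time in pregnancy or before it.

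Collection after delivery says when the record is read. It does not say which part of the record counts. Sections 8d and 12 both place the booking appointment before study contact and the scan, and Appendix 2 takes booking values from the records. The record being read therefore includes time before the measurement.

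At stake is what the c-index for this outcome means. If cases from before the visit are mixed in, the figure partly describes association with past infection instead of prediction of new infection. If infection enters the composite, whose components the protocol does not list, the mixture carries over.

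**Working it through.** The protocol gives no infection rate, no share recorded before the visit and no target c-index for this outcome, so there is no stated figure to reproduce. The check has two parts.

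**1. Is there a window or date anywhere?** Infection appears in three places: the outcome list of the Protocol Summary (Section 5), the outcome list of Section 8f, and Appendix 2.

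| Outcome | Time limit in 8f | Timing collected in Appendix 2 |
|---|---|---|
| Gestational hypertension | after 20 weeks | gestation at onset |
| Pre-eclampsia | new, after 20 weeks | gestation at onset |
| Gestational diabetes | none stated | gestation at diagnosis |
| Haemorrhage | third stage and immediate postpartum | fixed by definition |
| Maternal infection | none | none |

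Of these five, only infection has neither a limit nor a recorded time.

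**2. What would early cases do to the c-index?** Let f be the share of counted cases that precede the visit, and assume that in those women the adiposity measure is distributed as in non-cases. The c-index is the chance that a random case scores higher than a random non-case. For the early cases that chance is 0.5, so

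observed c = (1 − f) × c + f × 0.5.

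For two measures with true values c₁ and c₂ the term f × 0.5 cancels:

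observed gap = (1 − f) × (c₁ − c₂).

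Take an assumed c of 0.65 for a rival measure and 0.62 for BMI, a true gap of 0.03. None of these values is from the protocol.

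| f | Rival | BMI | Gap |
|---|---|---|---|
| 0% | 0.650 | 0.620 | 0.030 |
| 10% | 0.9 × 0.65 + 0.05 = 0.635 | 0.9 × 0.62 + 0.05 = 0.608 | 0.027 |
| 30% | 0.7 × 0.65 + 0.15 = 0.605 | 0.7 × 0.62 + 0.15 = 0.584 | 0.021 |
| 50% | 0.5 × 0.65 + 0.25 = 0.575 | 0.5 × 0.62 + 0.25 = 0.560 | 0.015 |

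Both measures fall and the gap narrows, but the order stays the same because both are scaled by the same factor. If early infections are related to adiposity, the formula does not apply and the direction could differ. The result would then be an association and not a prediction.

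**The case against.** The strongest reply is that the protocol never says earlier infections will be counted. In every list the item follows retained placenta and haemorrhage, which suggests infection around the birth, and Section 8g speaks of women who develop the outcome. Exact windows and codes for an outcome taken from records are often left to the analysis plan or a data dictionary, which are not shown. It is also one outcome among about 20, is not named as primary, and does not drive the sample size, which Section 8e bases on pre-eclampsia.

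Part of this stands. The fault is a failure to exclude, and a reader who infers that the protocol instructs the team to count earlier infections goes beyond the text. The documents also do not say which infections are logged at booking. But someone extracting data cannot rely on list order, and deferral to the analysis plan does not fully answer the point. A later window needs a date, and Appendix 2 lists none. Section 9 sends anonymised data for analysis once follow-up collection is complete, so dating the item then would mean going back to the records.

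A reader might also infer that metabolic syndrome has the same fault, since one component is "high blood pressure that's consistently 140/90mmHg or higher" with no start date. The documents do not support that. Three of four measures are needed, so blood pressure together with BMI or waist is not enough: at least one of triglycerides or insulin resistance must also be met. Appendix 2 takes triglycerides and fasting insulin from the glucose tolerance test, whose gestation is collected. It also lists booking blood pressure and essential hypertension, so hypertension already present can be identified. Counting only components first met after the visit would void the BMI or waist component for women who already meet it there. Leaving such women out would remove those with overweight or obesity (21% + 28% = 49% on the national figures in Section 6), the group the study is about.

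**Conclusion.** The point holds in a limited form. As worded, the definition does not exclude infections recorded before the 12-week visit, and the data items as listed give no means of removing them afterwards. This conflicts with the prognostic aim, and it falls short of the timing that the protocol specifies or collects for its other maternal complications.

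The size cannot be fixed from the documents because f is unknown. If early cases are unrelated to adiposity, differences from BMI shrink by (1 − f), which is 10% to 50% of the true difference over the range shown. One might infer that this could hide or reverse an advantage over BMI. The arithmetic does not support that: a lower absolute c-index for one measure says nothing about its standing against BMI when both move together, and the ranking is unchanged.

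The weight is minor to moderate. Outcomes are modelled separately (Section 8g), so the effect stays within one outcome unless infection is part of the composite.

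**What to change.** In Section 8f, define maternal infection as a new infection first recorded after the date of the research visit and up to maternal discharge after birth. In Appendix 2, add the date or gestation of infection beside the existing item, as is done for gestational diabetes and for hypertension and pre-eclampsia.

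The cost is one extra extracted field, one sentence in the protocol, and fewer counted events, by an amount that depends on f. The change is cheapest before outcome extraction, since afterwards it would mean returning to the records. Metabolic syndrome needs no change on this account.

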Measurements of subcutaneous and visceral fat will be performed by trained operators (sonographer) using a GE E8 ultrasound machine with 2-5 MHz curvilinear probe. Methods described by Martin *et al.* (27) will be used to obtain the measurement. Ultrasound settings and patient position will be standardised to insure consistency of the procedure. Further, image capture will be standardised for breathing movements (on expiration) and bladder filling. Midline transverse section of the maternal abdomen will be obtained approximately 1 cm above the umbilicus to allow visualisation of transverse section of the abdominal aorta at the far field of the screen.

- Subcutaneous fat (SAT) measurement will be obtained from outer border of the subcutaneous fat layer to the outer border of rectus abdominus at the level of linea alba.
- Visceral fat (VAT) measurement will be obtained from the inner border of rectus abdominus at the level of linea alba to the anterior wall of the aorta.
- Total abdominal fat (TAT) will be calculated as a sum of SAT and VAT.

Three consecutive measurements will be performed and average of three will be employed in the predictive model. In a small sub-set of participants, measurement will be repeated by a second operator to assess inter-rater reliability of the ultrasound technique.

In addition to the above measurements of SAT and VAT, an alternative method of measuring these by ultrasound will be deployed to establish optimal methods for future implementation. SAT and VAT will be measured at the sagittal plane of xiphisternum as described by Cremona *et al* (28).

Anthropometry:

- Waist circumference, measured at the narrowest point of the abdomen between the lower costal (10th rib) border and the top of the iliac crest, perpendicular to the long axis of the trunk, at the end of normal expiration and with the abdominal muscles relaxed, to the nearest 0.1 centimetre.
- Hip circumference, measured at the greatest posterior protuberance of the buttocks, perpendicular to the long axis of the trunk, with the gluteal muscles relaxed and the feet together, over light clothing and to the nearest 0.1 centimetre.
- Height will be measured to the nearest 0.1 centimetre with shoes removed and the participant's head positioned in the Frankfort plane.
- Weight will be measured, in light clothing to the nearest 100g.

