- Neck circumference, measured immediately superior to the thyroid cartilage and perpendicularly to the long axis of the neck with the head in the Frankfort plane, to the nearest 0.1 centimetre.
- Mid upper arm circumference, measured at the midpoint of the upper arm between the acromiale and radiale, perpendicular to the long axis of the arm, to the nearest 0.1 centimetre.
- Skinfold thicknesses (subscapular, triceps, biceps, iliac crest and supraspinale) measured using Harpenden skinfold callipers. Sum of skinfolds will be calculated using these measurements.
- Waist to hip ratio, waist to height ratio, BMI, Body Adiposity Index, A Body Shape Index (ABSI), Hip Index, Weight-Adjusted Waist Index, Body Roundness Index, Abdominal Volume Index, Conicity Index, Estimated Total Body Fat, Relative Fat Mass, CUN-BAE and body fat percentage will be calculated from these measurements. If any additional composite adiposity measures/indices become available in the literature that can be calculated by the data we have collected then we will explore whether to include these in our analysis.
- Self-reported body shape using a visual scale for body shapes

Measurements will be taken, directly on the skin unless otherwise specified above, on the right side of the body unless impracticable due to injury in which case the left side may be used. All anthropometric measurements will be taken by individuals who have received ISAK training (<https://www.isak.global/>). Measurements will be taken

in duplicate, and a third measurement undertaken if the difference between the first two measures is greater than 5% for skinfolds or 1% for other measures. If two measures are taken, the mean value will be used in data analysis. If three measures taken, the median value will be used.

Other predictor variables

A number of other variables that have previously been reported to be associated with pregnancy outcome will be collected by questionnaire or from routine records:

- a. Socio-demographic:
 - a. maternal age
 - b. parity
 - c. ethnic group
 - d. Index of Multiple Deprivation score (derived from postcode)
- b. Clinical:
 - a. This pregnancy/booking data (e.g. blood pressure, smoking, alcohol consumption)
 - b. Past obstetric history (previous gestational diabetes (GDM), pregnancy hypertension, caesarean section, macrosomia)
 - c. Other medical history (pre-existing type 1/type 2 diabetes, hypertension, bariatric surgery)
 - d. Family history of diabetes

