- Apgar scores at 1 and 5 minutes (score 1-10); as reported in medical records.
- Jaundice: as reported in medical records.

- Respiratory distress (including requiring resuscitation): as reported in medical records.
- Feeding method (first feed and feed method at discharge): breastfeeding or artificial feed; as reported in medical records.
- Admission to neonatal special care baby unit (SCBU) or intensive care unit (NICU), high-dependency care, transitional care; as reported in medical records.

In addition, information on any reason for loss to follow up (e.g. late miscarriage, stillbirth, or participant moving to another area) will be sought from medical records in order to account for missing outcome data.

g. Analysis

The aim of the analysis is to explore if any single adiposity measure taken in this study performs better than BMI in terms of predicting women at high-risk of an adverse pregnancy outcome. Each adiposity measure will be assessed individually. If no one measure performs better than BMI, multiple logistic regression models will be used for the analysis of each outcome separately. There won't be any variable selection since our predictors are already fixed. Wherever possible, we will retain continuous candidate predictors in their continuous form to avoid statistical power loss (29). Nonlinear trend in continuous predictors will be explored using either fractional polynomials or restricted cubic splines.

The apparent performance of the developed model will be summarised using calibration, discrimination and internal validation analyses (30). Calibration determines performance in terms of the agreement between the probability of developing the outcome as estimated by the measure/model, and the observed outcome frequencies. Discrimination is the measure of the model's ability to distinguish between individuals who develop the outcome or not (i.e., a higher probability assigned to the individual who develops the outcome compared with an individual who does not. This will be assessed using the c-index (equivalent to the area under the receiver operating characteristic [AUROC] curve).

Any missing values will be assumed to be missing at random (MAR) and multiple imputation (MI) will be implemented using 20 imputations (31). Calibration and discrimination of the developed model(s) will be summarised in the datasets

(averaged over imputation datasets). Calibration will also be assessed graphically (32).

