The model will be internally validated using bootstrap re-sampling method in order to quantify the degree of optimism due to overfitting (33, 34) and to derive optimism-adjusted indices of discrimination (c index) and calibration (calibration slope) (35). Two hundred bootstrap samples will be used (36). Optimism is expected when measures/models are applied to the same dataset used for development, as they have been developed to achieve the best fit for that specific dataset (i.e., overfitting). Statistical techniques (e.g., bootstrapping) can quantify the potential for overfitting, and provide adjustment estimates (e.g., shrinkage factor) to reflect the prognostic performance in a new dataset/population.

9. Data storage and management

Data handling, record keeping and access to data

Participant identifiable information will be handled in line with GDPR 2018 principles. Initial data collection and storage will be via Redcap and data will be stored on the NUTH secure server under Caldicott approval until recruitment is complete. At the end of the recruitment period data will be anonymised. All participants will be given a unique identifier to facilitate this. Following completion of all follow up data collection (i.e. from routine maternity records), anonymised electronic research data will be transferred to a Newcastle University secure server for analysis. No personal identifying information will be presented in the study outputs.

The clinical research team and local R&D monitors may require access to the participants' clinical notes; participants will be informed of this in the participant information sheet, and permission to do so will be obtained as part of the consent process.

Archiving

For women who have consented to the SHAPES study, data will be stored securely with restricted access for a period of 5 years after the end of the study. Any

identifiable data will be stored by NUTH, and anonymised research data stored by Newcastle University on a secure server.

Future research: long-term follow-up

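### Section 8g makes the multivariable models depend on no single measure beating BMI, which conflicts with Objective 2 and leaves that decision open to a chance winner among 31 measures

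*Protocol*

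**What the plan says.** Section 7 (repeated in the section 5 summary) gives Objective 2 without a condition: "To develop a prognostic model to investigate the effect of including multiple adiposity, socio-demographic and clinical predictors on the accuracy of predicting outcomes". The Aim is looser: "To evaluate the prognostic performance of single adiposity measures or a multivariable model to estimate risk of adverse pregnancy outcomes". Section 8e bases the sample size on a model with at most 7 variables for preeclampsia and reports a minimum of 980 women against 1400 planned.

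Section 8g describes the analysis as a search for any single measure that predicts better than BMI. "Each adiposity measure will be assessed individually", and then: "If no one measure performs better than BMI, multiple logistic regression models will be used for the analysis of each outcome separately". It gives no margin, interval or test for that judgement and does not say whether a win on one outcome is enough. It also states that no variables will be selected, because the predictors are fixed.

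Section 8f lists the measures. It includes sums of other measures ("Total abdominal fat (TAT) will be calculated as a sum of SAT and VAT"), a second ultrasound method ("SAT and VAT will be measured at the sagittal plane of xiphisternum") and an invitation to extend the list: "If any additional composite adiposity measures/indices become available in the literature that can be calculated by the data we have collected".

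On validation, section 8g says: "The model will be internally validated using bootstrap re-sampling method in order to quantify the degree of optimism due to overfitting". Objective 3 and the later text of 8g apply performance testing to single measures as well as models. Neither mentions repeating the choice of the best measure. Section 11 says that the variables that predict best will go forward to an individual participant data meta-analysis.

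**The concern.** Two things are at stake.

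The first is consistency. Objective 2 asks what adding several adiposity, socio-demographic and clinical predictors does to accuracy. A result that one measure beats BMI cannot answer that. A rule that turns to multivariable models when no measure wins therefore leaves one of three objectives unanswered whenever a measure does win, even if the win is genuine.

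The second is chance. Comparing many alternatives with one reference and acting on the best is a selection step, whatever the protocol says about variable selection. The best of many sample c-indices is biased upwards. Internal validation that takes the winner as given does not see that bias. A false winner could both displace the multivariable analysis and be carried into the later meta-analysis as a leading variable.

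**Working it through.** **1. The protocol's own figure.** Inputs from section 8e: 7 predictors, shrinkage of at most 10% (S = 0.9), c-index 0.80, prevalence 5-6%. The shrinkage criterion is n = P / [(S - 1) ln(1 - R²/S)], with R² the Cox-Snell value implied by the c-index and prevalence under a binormal linear predictor. At 5%, R² = 0.0623 and n = 7 / [(-0.1) × ln(1 - 0.0623/0.9)] = 976, which reproduces the stated 980. At 5.5% n = 895 and at 6% n = 828. With 1400 women and 5% prevalence there are 70 events, or 10 per predictor. Fitting the 7-variable model for every outcome therefore needs no extra recruitment.

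**2. Number of measures (section 8f).** Ultrasound: 3 (subcutaneous, visceral, total) + 2 (second method) = 5. Direct anthropometry: 6. Skinfolds: 5 sites + their sum = 6. Derived indices: 14 listed less BMI = 13. Self-reported body shape: 1. Total 5 + 6 + 6 + 13 + 1 = 31. Leaving out height and weight gives 29.

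**3. Numerical comparison.** If BMI and K alternatives are exchangeable, BMI ranks first with probability 1/(K + 1). So the chance that at least one alternative looks better is K/(K + 1): 31/32 = 96.9% for 31 measures, 29/30 = 96.7% for 29, and 10/11 = 90.9% for 10.

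**4. Simulation.** 1400 women and 1500 simulated studies per setting. Assumptions not in the protocol: true c-index 0.65 for every measure including BMI, equal pairwise correlations of 0.5, 0.7 or 0.9, and a 15% event rate as a second scenario. The 5.5% rate is the midpoint of the protocol's 5-6%. The test column counts a two-sided 5% DeLong test in favour of any alternative, without adjustment.

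| Event rate | Correlation | Any higher c-index, 31 (10) measures | Any unadjusted test win, 31 (10) measures | Mean apparent gain, best of 31 |
|---|---|---|---|---|
| 5.5% | 0.5 | 97.1% (91.6%) | 26.9% (15.1%) | 0.047 |
| 5.5% | 0.7 | 98.0% (91.7%) | 26.3% (15.0%) | 0.038 |
| 5.5% | 0.9 | 96.6% (90.9%) | 27.9% (15.1%) | 0.022 |
| 15% | 0.5 | 96.7% (89.9%) | 25.1% (14.9%) | 0.030 |
| 15% | 0.7 | 97.7% (90.5%) | 26.7% (14.5%) | 0.024 |
| 15% | 0.9 | 96.9% (90.3%) | 26.5% (14.6%) | 0.014 |

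Correlation shrinks the false gain but hardly changes how often it occurs. At 5.5%, if all 31 measures are truly worse than BMI by 0.01, one still looks better in 85-93% of studies; if worse by 0.02, in 56-87%.

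**5. What the bootstrap sees.** Under the same kind of simulation, resampling the already chosen measure gave an optimism within ±0.002, although the true gain was zero and the apparent gain was up to 0.047. The c-index of a single linear predictor depends only on ranks, so refitting it has almost nothing to correct. Repeating the choice in every resample recovered roughly two thirds of the false gain.

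**The case against.** Several points on the other side stand.

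- A reader might infer that the study would nearly always declare a winner by chance. The protocol does not support that flatly. The 97% belongs to a purely numerical comparison, and section 8g leaves the criterion open. A SAP may set one, and a margin or adjustment would bring the chance below the 25-28% for unadjusted tests. Section 8g also looks at calibration, which the simulation ignores.
- A reader might infer that Objective 2 is cancelled outright. Section 8g does not say that the models are fitted in no other case, and the Aim's choice between single measures and a model gives some support to a stepwise plan. It softens the conflict with Objective 2 and section 8e but does not remove it.
- A reader might infer that the bootstrap leaves single measures out. Objective 3 and section 8g bring them in. Only the repetition of the choice is absent.
- A reader might infer that the later validation and economic work depends on the multivariable models. Section 11 ties validation to the best predicting variables and the economic work to the alternative approach in general. The meta-analysis may expose a false winner, but it would not restore a model that was never fitted.
- Multiplying 31 measures by 20 outcome headings to get 620 comparisons is not sound. Fetal growth, Apgar scores and blood loss in ml are not binary as defined. The measures also overlap heavily, although 10 effective measures still give about 90% and 15%.

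**Conclusion.** The inconsistency between section 8g and both Objective 2 and section 8e holds under any definition of beating BMI and must be resolved. Read as written, one winning measure leaves Objective 2 unanswered.

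The openness to chance is real, but its size is conditional. Per outcome, if no measure is truly better, the chance of a false winner among 31 runs from about 25-28% (unadjusted tests) to about 97% (numerical comparison). The winner's apparent gain averages about 0.02-0.05 in c-index at 5.5% prevalence and would go largely uncorrected unless the selection is repeated or otherwise guarded against. These sizes rest on the assumed c-index of 0.65 and equal correlations of 0.5-0.9. This second part is secondary to the inconsistency, because a SAP could narrow it.

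**What to change.** 1. Delete the condition in section 8g. Fit the Objective 2 model for every outcome suited to logistic regression, with a BMI-based model as reference.
2. Report each measure's paired c-index difference from BMI with an interval. Protect any claim of superiority over BMI against selection, either by repeating the choice of the best measure inside each bootstrap resample or by a prespecified margin or multiplicity control. Any of these is acceptable. Repeating the choice removes most but not all of the bias.
3. Fix the list of measures on which such a claim may rest before outcome data are linked, and label later additions exploratory.

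The cost is analysis wording and computing time. Recruitment is unchanged (1400 planned, 980 stated minimum). Fewer measures will be declared better than BMI.
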